5.4 Concomitant Medication Treatment		
721-723	Any use of toothpicks and/or floss around the treated implant/s in the 24 hours following the chip insertion.	Any use of toothpicks and/or floss around the treated implant/s in the 24 hours following the chip insertion and advised to use such interproximal cleaning devices only to negotiate food impaction for the following 6 days.
6. Study Plan - Treatment 1: (PerioChip®)		
742-745	Subgingival debridement will be carried out for each one of the target implant which its probing pockets depth (PD of 5-8 mm) were selected as target pockets (The Subgingival debridement procedure will be employ twice: at baseline (visit 2) and after 3 months, at visit 8).	Subgingival debridement will be carried out for each one of the target implant which its probing pockets depth (PD of 5-8 mm) were selected as target pockets (the Subgingival debridement procedure will be employed twice: at baseline (visit 2) and after 3 months, at visit 8).
6.1 Study Schedule		
764-772	
Evaluations/Activity Column: "dental Radiography SuperScript #1: Dental Radiography evaluation dated within 1 (one) year prior the Screening visit SuperScript #2: In case chips are pop-out recurrently in visits 3, 5 and 7 a pocket examination will be conducted by the designated examiner to
	
Evaluations/Activity Column: "Periapical dental Radiography. SuperScript #1: "Periapical Dental Radiography evaluation dated within 1 (one) year prior the Screening visit. SuperScript #2: In case chips are pop-out recurrently in visits 3, 4, 5 and 7 a pocket examination will be conducted by the designated

Dexcel Pharma Technologies Ltd

	verify PD \geq 5 mm SuperScript #6: Chip/s will be inserted only in target implant/s which had previously received a chip and which pocket depth at those visits is \geq 5 mm	examiner to verify PD \geq 5 mm SuperScript #6: Chip/s will be inserted only in target implant/s which had previously received a chip
6.2.1 Screening Visit and Hygienic Phase Therapy (Weeks (-3 to -1))		
788-798	radiographic evaluation dated within 1 (one) year prior the Screening visit	periapical radiographic evaluation dated within 1 (one) year prior the Screening visit
6.2.2 Baseline Visit (Week 0)		
893-899	Subgingival debridement will be carried out for all the chosen target implant/s, regardless of the study arm randomization. The Subgingival debridement is the removal of all local irritants from the periodontal pockets and implant surface including the inflammatory tissue. The procedure will be carried out using metal based curettes and ultrasonic management and irrigation with Chlorhexidine ("blasting" cleaning is prohibited).	Subgingival debridement will be carried out for all the chosen target implant/s, regardless of the study arm randomization. The Subgingival debridement is the removal of all local irritants from the periodontal pockets and implant surface including the inflammatory tissue. The procedure will be carried out using metal based curettes and possibly ultrasonic management and/or irrigation with Saline ("blasting" cleaning is prohibited).
918-925	Oral Hygiene instructions - The Investigator or designee will remind the patient of the importance of good hygiene of the mouth (if necessary) and of the restriction of use of Chlorhexidine oral rinses/mouthwashes. In addition the patient will be instructed to refrain from use of toothpicks and/ or in the 24 hours following the chip insertion.	Oral Hygiene instructions - The Investigator or designee will remind the patient of the importance of good hygiene of the mouth (if necessary) and of the restriction of use of Chlorhexidine oral rinses/mouthwashes. In addition the patient will be instructed to refrain from use of toothpicks and/ or floss at least for the 24 hours following the chip insertion, and advised to use such interproximal cleaning devices only to negotiate food impaction for the following 6 days.
928-929		The period between Baseline visit and Visit 3 should not exceed 14 ± 4 days
6.2.3 Visits 3, 4, 5, 6, 7 and 8 (Weeks 2, 4, 6, 8, 10 and 12)		
949	Supragingival Scaling (at week 12 only)	Supragingival Scaling (at week 12 (Visit 8) only).
951-952	Pocket examination and measurements (i.e. PD, R and BOP) only for the target implant/s (only at weeks: 8 and 12)	Pocket examination and measurements (i.e. PD, R and BOP) only for the target implant/s (only at weeks: 8 and 12 (visits 6 and 8)).
954-956	Subgingival debridement will be carried out for all the chosen target implant/s, regardless of the study arm randomization, (at week 12 only).	Subgingival debridement will be carried out for all the chosen target implant/s, regardless of the study arm randomization, (at week 12 (Visit 8) only).
957-966	Chip/s insertion only in those target pockets which had previously received a chip and which pocket depth is \geq 5 mm. In case chips are pop-out recurrently in visits 3, 4, 5 and 7 a pocket examination will be conducted by the designated examiner to verify PD \geq 5 mm. The examiner will then declare "please try to restore again" if PD \geq 5 mm or "do not proceed with the insertion".	Chip/s insertion only in those target pockets which had previously received a chip. For visits 6 and 8, chip insertion will follow pocket depth verification of \geq 5 mm as measured during the visit. For visits 3, 4, 5 and 7, in case chips pop-out recurrently a pocket examination will be conducted by the designated examiner to verify PD

Dexcel Pharma Technologies Ltd

		≥ 5 mm. The examiner will then declare "please try to insert again" if $PD \geq 5$ mm or "do not proceed with the insertion".
967-974	Oral Hygiene instructions - The Investigator or designee will remind the patient of the importance of good hygiene of the mouth (if necessary) and of the restriction of use of Chlorhexidine oral rinses/mouthwashes. In addition the patient will be instructed to refrain from use of toothpicks and/ or in the 24 hours following the chip insertion.	Oral Hygiene instructions - The Investigator or designee will remind the patient of the importance of good hygiene of the mouth (if necessary) and of the restriction of use of Chlorhexidine oral rinses/mouthwashes. In addition the patient will be instructed to refrain from use of toothpicks and/ or floss at least for the 24 hours following the chip insertion, and advised to use such interproximal cleaning devices only to negotiate food impaction for the following 6 days.
6.2.4 Visits 9 (Week 16)		
995-996		The allowed window for visit 9 should not exceed 28 ± 4 days from the previous visit.
6.3.1 Calibration of Examiners		
1013-1015	PD and R measurement procedures will be standardized between medical centres and investigators prior to study initiation, consistent with Good Clinical Practice (GCP).	PD and R measurement procedures will be standardized between investigators within each medical centre prior to study initiation, consistent with Good Clinical Practice (GCP).
7.2 Randomization Codes		
1044-1045	A total number of 56 blocks will be prepared for a total of 336 subjects.	Line removed
1050	This number already includes 10 blocks for spare	Line removed
7.3 Blinding		
1055-1059	Subgingival debridement only	Subgingival debridement alone
8.1 Sample Size		
1070-11077	A total of 246 patients will be randomized, 123 patients for the Subgingival debridement + PerioChip® arm and 123 patients for the Subgingival debridement alone arm. Based on previous phase IIa studies, the expected drop-out rate in this study will be between 20%-25%. Thus, it is estimated that approximately 336 patients will be screened in order to randomize 246 patients.	A total of up to 290 patients will be randomized, in order to analyse at least 123 patients in the Subgingival debridement + PerioChip® arm and at least 123 patients in the Subgingival debridement alone arm, considering expected patient drop-out rate estimation of between 12%-15%. Based on previous phase IIa studies, the expected drop-out rate in this study will be between 20%-25%. Thus, it is estimated that approximately 375 patients will be screened in order to randomize up to 290 patients, of which 246 patients will complete all required study visits.

1. INTRODUCTION

1.1 Objectives

This document details the statistical analysis that will be performed for the Dexcel Pharma Technologies, Ltd. study CLI/016P. The statistical methods described in the SAP are elaboration of the statistical section included in the study protocol.

The primary objective of the study is to compare the mean probing Pocket Depth (PD) reductions (absolute change) for the selected target implant/s at week 24 compared to baseline.

The secondary objectives of the study are:

- PD measurement at week 24 compared to baseline in patients with baseline PD measurement of 6-8 mm inclusive.
- Bleeding on Probing (BOP) measurements at week 16 and 24 compared to baseline.
- PD measurement at week 16 compared to baseline

The exploratory objectives of the study are:

- PD, BOP and Relative Attachment Levels (RAL) measurements at week 24 compare to baseline in Responders patients. Responder patients are those patients which demonstrated at week 24 PD reduction of at least 1 mm from baseline PD of 5 mm or PD reduction of at least 2 mm from baseline PD of 6-8 mm inclusive.
- PD and BOP measurements at weeks 8 and 12 compared to baseline.
- Recession (R) and RAL measurements at weeks 8, 12, 16 and 24 compare to baseline.
- PD measurement at week 12 and 16 compared to week 24.
- PD, BOP, RAL and R measured at weeks 8, 12, 16 and 24 for all 4 sites (mesio-buccal, mid-buccal, disto-buccal and mid-lingual), surrounding the selected target implant/s, compared to baseline.

The safety objective of the study is to assess the safety of the PerioChip®.

1.2 Design

This study is a multi-center, randomized, single-blind masking, parallel, two-arm clinical study.

The study duration will be 25-28 weeks (6 months) and will comprise a total of 10 visits: Screening and hygienic phase therapy (weeks -3 to -1), Baseline (week 0), week 2, week 4, week 6, week 8, week 10, week 12, week 16 and week 24 (follow up visit).

During the Baseline visit, eligible patients will be randomized to one of the following treatment regimens:

Treatment 1 – Subgingival debridement + Chlorhexidine Gluconate chip (PerioChip®) inserted every fortnight, for the first 12 weeks.

Treatment 2 – Subgingival debridement.

These treatments will be applied for at least 1 (one) and not more than 2 (two) implants in the oral cavity with clinical and radiographical signs of peri-implantitis. Peri-implantitis is defined as marginal bone loss of at least 3 mm from implant shoulder, and at least 2 mm distal and mesial supporting bone left from the apex to the coronal direction, in combination with bleeding and/or suppuration on probing and a peri-implant Probing Depth (PD) of 5-8 mm.

All pocket measurements (PD, BOP and R) and chip insertions will be made in the same order of procedures every time.

The same examiner will perform all the measurements during the study.

The person (physician/hygienist) placing the Chlorhexidine chips in the periodontal pockets or performing the Subgingival debridement, according to the randomization, will not be involved in target pockets measurements (i.e. the examiner and the physician/hygienist placing the chip or performing the Subgingival debridement will be two different persons).

In each patient meeting the entrance criteria, the deepest periodontal pocket of at least 1 (one) and no more than 2 (two) implant/s (if available) will be selected as a target pocket, and will be used for chip/s insertion or Subgingival Debridement and as the primary efficacy end-point.

The target pocket in the selected implant/s, will be treated at each visit with the same treatment arm, initiated at Baseline visit, as described below.

Implant/s which were not selected as target implant/s will be treated as per the investigators discretion as long as it does not affect the study inclusion/exclusion criteria (e.g. treatment with antibiotics or surgery next to a target implant included in the study).

Treatment 1: (PerioChip®)

Subgingival debridement will be carried out for each one of the target implant which its probing pockets depth (PD of 5-8 mm) were selected as target pockets. The Subgingival debridement procedure will be employ twice: at baseline (visit 2) and after 3 months, at visit 8.

Upon completion of the debridement a PerioChip® will be inserted in each one of the target implant.

PerioChip® contains 2.5 mg Chlorhexidine Gluconate formulated in a biodegradable cross linked gelatine matrix. The maximum dosage for each implant is 5 mg Chlorhexidine Gluconate (i.e. up to 2 PerioChips can be inserted to one implant) and 10 mg of Chlorhexidine Gluconate for each patient per visit. The total number of PerioChips that can be inserted to one patient in one given visit will not exceed 4 PerioChips.

The number of chips inserted to one implant will be a function of the pocket width. In case 2 chips are used in one implant, the insertion will be to the target pocket and the implant surface which is not adjacent to the target pocket (i.e. Buccal - Lingual or Mesial - Distal).

The insertion place should be recorded in the Source Document. All subsequent insertion must be repeated to the exact place chosen in the first insertion procedure.

Treatment 2: (Subgingival Debridement)

Subgingival Debridement will be carried out for each one of the target implant which its probing pockets depth (PD of 5-8 mm) were selected as target pockets.

The Subgingival debridement procedure will be employ twice: at baseline (visit 2) and after 3 months, at visit 8.

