Page 40 - Randomization Code	The randomization will be performed with stratification to study sites smoking habits and Baseline PD measurement in balanced blocks, each block containing 6 subjects. A total number of 48 blocks will be prepared for a total of 288. Each site will receive 4 types of lists by the defined stratification (smokers with PD 5 mm, smokers with PD 6-8 mm, non-smokers with PD 5 mm and non-smokers with PD 6-8 mm). This number already includes 10 blocks for spare.	The randomization will be performed with stratification to study sites smoking habits and Baseline PD measurement in balanced blocks, each block containing 6 subjects (3 per treatment Subgingival debridement + PerioChip® and 3 per treatment Subgingival debridement alone). A total number of 56 blocks will be prepared for a total of 336 subjects. Randomization blocks will be sent to the sites by the study data management Statistician . Each site will receive 4 types of lists by the defined stratification (smokers with PD 5 mm, smokers with PD 6-8 mm, non-smokers with PD 5 mm and non-smokers with PD 6-8 mm). Additional blocks will be provided to the sites according to the recruitment rate . This number already includes 10 blocks for spare.
Page 41 – Sample size	Statistical significance level was set to 4% since an Interim Analysis, that will use 1% of the total significance level, is planned.	Statistical significance level for all statistical analysis was set to 4% since an Interim Analysis that will use 1% of the total significance level, is planned 5.
Page 42 - Analysis population	Intent-to-treat (ITT) population – all patients randomized for one of the treatment arms and treated with at least one chip of study treatment or underwent Subgingival debridement will be used for all safety evaluations	Intent-to-treat (ITT) population – all patients randomized for one of the treatment arms and treated with at least one chip of study treatment or underwent Subgingival debridement will be used for assessments related to efficacy and all safety evaluations

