148-151	A total of 246 patients in at least five clinical sites will be randomized. 123 patients for the Subgingival debridement + PerioChip® arm, and 123 patients for Subgingival debridement alone arm	A total of 290 patients in at least nine clinical sites will be randomized. At least 123 patients for the Subgingival debridement + PerioChip® arm, and at least 123 patients for Subgingival debridement alone arm will complete all required study visits, considering withdrawal rate estimation of between 12%-15%
Protocol Synopsis - Inclusion Criteria #5		
177-183	The patient has at least one implant in the oral cavity with clinical and radiographical signs of peri-implantitis. In the affected implant, at least one of the four aspect measured (mesio-buccal, mid-buccal, disto-buccal and mid-lingual) must show radiographic evidence of bone loss of at least 3 mm from implant shoulder, and at least 2 mm distal and mesial supporting bone left from the apex to the coronal direction, in combination with bleeding and/or suppuration on probing and a peri-implant Probing Depth (PD) of 5-8 mm.	The patient has at least one implant in the oral cavity with clinical and radiographical signs of peri-implantitis. In the affected implant, at least one of the four aspects measured [mesio-buccal (MB), mid-buccal (MiB), disto-buccal (DB) and mid-lingual (MiL)] must show radiographic evidence of bone loss of at least 3 mm from implant shoulder, and at least 2 mm distal and mesial supporting bone left from the apex to the coronal direction, in combination with bleeding and/or suppuration on probing and a peri-implant Probing Depth (PD) of 5-8 mm.

Dexcel Pharma Technologies Ltd

Protocol Synopsis - Exclusion Criteria #10		
204-207	Patients chronically (i.e. two weeks or more) treated with non-steroidal anti-inflammatory drugs (NSAIDs) or any medications known to affect soft tissue condition (excluding treatment of Acetylsalicylic acid \leq 100 mg/day).	Patients chronically (i.e. two weeks or more) treated with non-steroidal anti-inflammatory drugs (NSAIDs) or any medications known to affect soft tissue condition (excluding treatment of Acetylsalicylic acid \leq 100 mg/day). A comprehensive list can be found in the Patient information sheet – list of prohibited medications.
Protocol Synopsis - Exclusion Criteria #11 (New)		

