3.4 Secondary Efficacy Endpoints

The secondary efficacy endpoints are:

- PD measurement at week 24 compared to baseline in patients with baseline PD measurement of 6-8 mm inclusive.
- Bleeding on Probing (BOP) measurements at week 16 and 24 compared to baseline.
- PD measurement at week 16 compared to baseline.

The analysis of the secondary endpoints will be based on ITT, mITT, PP and PP2 populations.

Multiplicity

The secondary efficacy endpoints will be analysed according to pre-defined order:

1. PD changes at 24 weeks from baseline in patients with baseline PD of 6-8 mm inclusive.
2. BOP changes at 24 weeks from baseline
3. BOP changes at 16 weeks from baseline
4. PD changes at 16 weeks from baseline

The following stages will be applied:

1. The 1st secondary endpoint in the ordered list will be tested at 5% significance level. If it achieves statistical significance then the 2nd secondary endpoint will be analysed (stage 2). Otherwise the other secondary endpoints in the list will not formally be tested.
2. The 2nd secondary endpoint in the ordered list will be tested at 5% significance level. If it achieves statistical significance then the 3rd secondary endpoint will be analysed (stage 3). Otherwise the other secondary endpoints in the list will not formally be tested.
3. The process will continue for all the secondary endpoints according to the list until a secondary endpoint is not significant or until all secondary endpoints have been found significant.

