Analysis for the number of pockets with at least 1 mm and at least 2 mm reduction in PD, and analysis for BOP for the target implant/s measured at each visit will be analyzed by a Chi-square test or Fisher's exact test as is appropriate.

Logistic regression will be applied for testing the above differences with adjustment to smoking status, GI, medical center and other suspected confounders, if found. Odds Ratio and 95% Confidence Interval will be calculated using the Logistic model.

Similar mixed models for PD, R and RAL with time as a fixed repeated covariate will be used to reveal the changes of these parameters over time.

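### BOP at weeks 24 and 16 is labelled change from baseline, but a target pocket need not bleed at baseline and the planned BOP tests do not name baseline BOP

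*SAP*

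**What the plan says.** **Eligibility.** In the protocol's version 6 to version 8 changes, amended Inclusion Criterion 5 requires that "at least one of the four aspects measured [mesio-buccal (MB), mid-buccal (MiB), disto-buccal (DB) and mid-lingual (MiL)] must show radiographic evidence of bone loss", "in combination with bleeding and/or suppuration on probing and a peri-implant Probing Depth (PD) of 5-8 mm". One aspect is enough, and suppuration can stand in for bleeding.

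**Target pocket.** SAP 1.2 says that "the deepest periodontal pocket of at least 1 (one) and no more than 2 (two) implant/s (if available) will be selected" as the target. No bleeding condition is attached, and the deepest pocket need not be the aspect that qualified the implant. The treatment paragraphs of the same section speak of each "target implant which its probing pockets depth (PD of 5-8 mm) were selected as target pockets".

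**Endpoint.** Step 2 of the ordered list in SAP 3.4 is "BOP changes at 24 weeks from baseline". Step 3 is the same quantity at week 16.

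**Analysis.** SAP 3.5 says the methods it sets out serve the primary and secondary endpoints; SAP 2.1 has near-identical text. For BOP these methods are a chi-square or Fisher test on BOP at each visit, and then: "Logistic regression will be applied for testing the above differences with adjustment to smoking status, GI, medical center and other suspected confounders". For PD, R and RAL, by contrast, the mixed model in SAP 2.1 and 3.5 lists the baseline measurement as a covariate, as does SAP 3.3.1 for PD.

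**The concern.** A test of BOP status at a visit measures change only if every target pocket bled at baseline, or if baseline status enters the analysis. The plan secures neither. Change in BOP could then mean prevalence at the visit, resolution among pockets that bled, or status adjusted for baseline, and the SAP does not say which.

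The week-24 BOP test is also a gate. If it fails, week-16 BOP and week-16 PD are not formally tested. A pocket dry at baseline cannot show resolution, so a share of such pockets may weaken the contrast, and an uneven share between arms shifts the observed difference. The primary endpoint is not affected.

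**Working it through.** **The plan's own figure.** Only PD is sized (SAP 1.8: difference 0.50 mm, SD 1.30, two-sided 5%, 85% power). Per arm, 2 × (1.960 + 1.036)² × 1.30² / 0.50² = 121.4, so 122 by the normal approximation; the t-test has 85.2% power at 123. The stated 123 reproduces, and nothing below alters it. Neither document gives a BOP rate or BOP power.

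**Can a target be BOP-negative?** Yes, by two routes.
- A pocket qualifies on suppuration alone and is the deepest.
- One aspect is 5 mm, bleeds and has the bone loss; another is 7 mm and does not bleed. The implant qualifies, and the 7 mm pocket is the target.

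**Does a stated BOP test use baseline BOP?** No. The visit test uses visit status. The logistic model names smoking, gingival index and centre, and leaves anything else to whether a confounder is suspected.

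**Size, on assumed rates.** All of these are assumptions: 123 per arm, one pocket per patient; week-24 BOP of 50% (debridement) v 33% (chip) in baseline bleeders; 15% in both arms in non-bleeders; share q of non-bleeding targets from 0 to 20%.

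Visit rate in each arm = (1 − q) × rate in bleeders + q × 0.15. With h = 2·arcsin√p₁ − 2·arcsin√p₂, power = Φ(h√(n/2) − 1.96).

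| q | Rates compared | Power, all targets | Bleeders per arm | Power, bleeders only |
|---|---|---|---|---|
| 0 | 0.500 v 0.330 | 77.7% | 123 | 77.7% |
| 10% | 0.465 v 0.312 | 69.6% | 111 | 73.4% |
| 20% | 0.430 v 0.294 | 60.6% | 98 | 68.0% |

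Example at q = 10%: h = 0.3154 and 0.3154 × √61.5 = 2.473, so power = Φ(0.513) = 69.6%. Restricting to baseline bleeders gains 73.4 − 69.6 = 3.8 points at 10% and 68.0 − 60.6 = 7.4 points at 20%.

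**Covariate adjustment.** On the same rates, 30,000 simulated trials per setting compared the unadjusted chi-square with a logistic likelihood-ratio test that adds baseline BOP. Power was 69.6% v 71.3% at q = 10% and 60.5% v 62.7% at q = 20%, a gain of about 2 points. Smaller runs of 2,000 to 3,000 trials gave gains of 1.7 to 2.5. With no treatment effect, the unadjusted test rejected in 4.6% and 4.5% of trials.

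**If the chip also acts in non-bleeders.** The same relative effect (0.33/0.50 = 0.66) gives 15% v 9.9% there. At q = 20% the chip rate is 0.8 × 0.33 + 0.2 × 0.099 = 0.284 against 0.430. Power is 67% for all targets and 68% for bleeders only, so almost nothing is lost.

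**Chance imbalance.** Take no treatment effect, week-24 BOP of 60% in bleeders and 25% in non-bleeders, and non-bleeding shares of 10% (debridement) and 20% (chip). Expected rates are 0.9 × 0.60 + 0.1 × 0.25 = 0.565 and 0.8 × 0.60 + 0.2 × 0.25 = 0.530, a spurious 3.5 points. Given that imbalance, a significant result favouring the chip has a chance of about 8%, against a nominal 2.5% in that direction.

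**The case against.** *The test is valid as it stands.* Targets are chosen by the same rule in both arms, and randomisation makes the unadjusted comparison sound on average. This stands. The 8% is conditional on one chosen imbalance; over all randomisations the error rate is near 5%. A reader might infer that the BOP result is biased, and neither the documents nor the simulation support that.

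*The plan may already cover it.* BOP is described for the target implant; if it were scored per implant, the route through a dry deepest pocket would close. But Tables 14.2-3.5 to 14.2-3.8 are by pocket, and the suppuration route stays open on either reading. The allowance for further suspected confounders permits baseline BOP but does not commit to it before the data are seen.

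*The gain is small and rests on assumed rates.* This also stands. The 4 to 7 points belong to the bleeders-only analysis, not to the covariate, and depend on no chip effect in non-bleeders.

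*A stronger reading.* A reader might infer that the plan admits targets deeper than 8 mm, or that sites could choose different pockets in the same mouth. The SAP describes target pockets as 5-8 mm, and the randomisation lists cover only "smokers with PD 5 mm, smokers with PD 6-8 mm, non-smokers with PD 5 mm and non-smokers with PD 6-8 mm". The responder definition likewise stops at 8 mm. Apart from ties, the deepest pocket is an objective choice. What remains is a gap: SAP 1.2 does not say how its two statements fit together when an implant qualifies on one aspect and has a pocket above 8 mm on another. The public protocol is only a summary of changes, so unamended text may settle that, and may also contain a bleeding condition.

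**Conclusion.** The point holds, at modest size and for the secondary endpoints only. As written, a target pocket can be BOP-negative at baseline, and the tests for the two BOP-change endpoints do not commit to using baseline BOP, although PD, R and RAL are adjusted for theirs. The consequences are an endpoint that does not match its label, some lost precision, and exposure to chance imbalance in a gated test. Type I error is not inflated overall.

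The size depends wholly on assumed BOP rates and an assumed 10-20% of non-bleeding targets. If no target is BOP-negative, there is no power loss and the label fits.

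**What to change.** 1. In SAP 2.1 and 3.5, name the target pocket's baseline BOP as a covariate in the week-16 and week-24 BOP logistic models.
2. Report, as a supporting analysis, BOP resolution at those weeks among target pockets that bled at baseline.
3. Reconcile the deepest-pocket sentence in SAP 1.2 with its 5-8 mm description of target pockets, for an implant that qualifies on one aspect and has a pocket above 8 mm on another. Because the chip is placed in the target pocket, no selection rule is proposed here; the sponsor should state which rule was in force.

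Items 1 and 2 cost a few words in the SAP and one extra table. BOP is already among the pocket measurements, so no new data are needed. They should be settled before unblinding. Item 3 is a clarification and does not re-select pockets already treated.
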